#### 1. BACKGROUND

Ryanodine receptor isoform 1-related myopathies (*RYR1*-RM) are rare, slowly progressive neuromuscular diseases. (1) They are the most common class of congenital myopathies caused by pathogenic variants in the ryanodine receptor isoform 1 (*RYR1*) gene and encompass a heterogeneous spectrum of histopathological and clinical subtypes. (1)

The *RYR1*-gene encodes a major skeletal muscle calcium (Ca2+) release channel – RyR1. RyR1 is embedded within the sarcoplasmic reticulum (SR) membrane of skeletal muscle and is a critical component required for effective skeletal muscle excitation-contraction coupling. (1, 2) Mutations within the *RYR1* gene result in chronic Ca2+ leak from the SR and primarily impair excitation-contraction coupling. (3, 4) Chronic Ca2+ leak into the sarcoplasm may lead to increased mitochondrial-related oxidative stress, RyR1 channel oxidation, cellular injury, leading to myopathy. (1, 5) Patients affected by *RYR1*-RM may experience mild to severe symptoms, ranging from delayed motor milestones, proximal muscle weakness, hypotonia, impaired ambulation, joint contractures, and fatigue to scoliosis, ophthalmoplegia, and respiratory involvement. (2, 3)

Both autosomal dominant (monoallelic, including *de novo* pathogenic variants) and recessive (biallelic) patterns of inheritance are reported to cause *RYR1*-RM. Although *RYR1*-RM has been associated with significant morbidities and early mortality, there is currently no approved treatment for this debilitating condition. Thus, there is a clear unmet need for therapies to treat *RYR1*-RM.

Rycals® are a novel class of Ca2+ channel stabilizers that are currently in clinical development. Under normal physiological conditions, Calstabin1 (FKBP12) binds and stabilizes the RyR1 closed state. (5) However, preclinical studies suggest that RyR1-Calstabin1 association is decreased in *RYR1*-RM, which exacerbates SR Ca2+ leak, resulting in detrimental downstream effects on muscle function. Rycals function as Ca2+ channel stabilizers by restoring RyR1-Calstabin1 binding when it is deficient, thereby stabilizing the RyR1 closed state. (5, 6)

The structural basis for mutations in RyR1 and the mechanism of action of ARM210 (S48168) on mutant forms of RyR1 has recently been elucidated. Using a series of cryo-electron microscopy (cryoEM) structures, Melville et al. (2022) identified a RyR1 binding site where the Rycal compound, ARM210 (S48168) binds cooperatively with adenosine triphosphate (ATP), stabilizes the closed state of the channel and prevents pathological pore opening. (7) ARM210 (S48168) is expected to be a disease-modifying therapy for *RYR1*-RM patients whose only defect is leaky RyR1.

Template No.: RWI\_TP\_EPI0011 Revision 2 Reference: RWI\_WI\_EPI0005

ARMGO Pharma, Inc. RYR1-RM Study Version 4.0 dated 10-SEP -2024 Protocol/Study No.: CL-EPI-001

Page 18 of 64

ARM210 (S48168) has completed Phase I clinical studies in healthy volunteers. ARM210 (S48168) is safe and well tolerated in single and multiple dose studies and has now been tested in 7 patients with *RYR1*-RM (NCT04141670). (8) Before progressing to Phase II, there is a need to define appropriate endpoints. This non-interventional study plans to provide evidence to support the optimal endpoints for a Phase II study in *RYR1*-RM patients.

#### 2. RATIONALE

Patients with RYR1-RM often have weakness in proximal muscle (closer to the trunk) movements rather than distal movements. (2) Improvements in shoulder abduction that involves proximal muscle have been observed in a Phase 1 clinical study with ARM210 (S48168). (9) This study aims to assess the extent to which the strength of movements is affected in participants with RYR1-RM with autosomal dominant mutations and the number of measurements for these movements to establish a stable baseline of the strength in these participants. These data will also be complemented and evaluated with added evidence from patient-reported outcome (PRO) measures. The study results will be used to inform anticipated variability and baseline measurements on the planned endpoints for a Phase II study. The findings from observed variability in muscle strength endpoints from this study will be compared to reference values obtained from the literature for healthy individuals. Muscle strength assessments in this study will be performed using Quantitative Muscle Assessment (QMA), Manual Muscle Testing (MMT), and Hand-Held Dynamometry (HHD). QMA is a computer-based system that tests muscle strength and fatigue by measuring the Maximum Voluntary Isometric Contraction (MVIC) of specific muscle movements. The participant pulls or pushes against a strap that is connected to an adjustable frame. The force measurements are compiled using a fixed dynamometer. This is the most quantitative method for measuring strength and will be used to determine the optimal endpoints to take into future studies. The endpoints selected for QMA are all proximal muscle movements that are often affected in RYR1-RM patients. In this study, endpoint measurements will be performed multiple times to determine how many separate measurements will allow for a stable baseline and to assess variability. It is expected that, with learning or education effect, participants may improve their performance on repeated measurements of the QMA endpoints as they become more familiar with the apparatus or procedure, without improving their strength per se. MMT, which is scored using a 0-5 point Medical Research Council (MRC) muscle strength scale, and HHD, an handheld device which also measures the MVIC generated from a muscle group, are two common methods to assess muscle strength in patients with myopathies in previous studies (10) and will be used in this study. The 10 Meter Walk Test (10-MWT), 1-Minute Sit-to-Stand Test, and Stair Climb Test are the additional tests to be conducted in this study to assess muscle strength and functionality. The 10MWT has been used to assess performance of patients with Duchenne Muscular Dystrophy (11) and the 1-Minute Sit-to-Stand Test has been used to assess both

Template No.: RWI\_TP\_EPI0011 Revision 2 Reference: RWI\_WI\_EPI0005

ARMGO Pharma, Inc. RYR1-RM Study Version 4.0 dated 10-SEP -2024 Protocol/Study No.: CL-EPI-001 Page 19 of 64

functional exercise capacity and quadriceps strength.  $(\underline{12}, \underline{13})$  The Stair Climb Test assesses the ability to climb a flight of stairs and lower extremity strength, power, and balance. (14, 15)

The study also seeks to describe PROs using the Patient-Reported Outcomes Measurement Information System (PROMIS)-Fatigue, PROMIS-Physical Function (PROMIS-PF), International Physical Activity Questionnaire (IPAQ), and symptom diary. Fatigue is one of the most predominant features of chronic illness. In the health outcomes measurement perspective, fatigue is defined as an overwhelming, debilitating, and sustained sense of exhaustion that reduces an individual's ability to carry out daily activities, including the ability to work effectively or function at optimally. (16) It is expected that information on the subjective experience of the participant collected using these PROs would complement the objective assessments conducted using QMA and other muscle strength tests. The PROMIS Fatigue scale will be used as a measure of fatigue severity in this study. Improvements in the PROMIS Fatigue scores for autosomal dominant patients were observed in the Phase 1 trial that was recently completed in RYR1-RM patients. Furthermore, the PROMIS Physical Function (PROMIS-PF) will be used as a measure of physical functioning, upper-extremity function, and mobility. RYR1-RM participants will also use a diary to capture their symptoms. Lastly, the Syde® device will be used in this study to objectively assess activity levels in ambulatory participants with *RYR1*-RM.

Template No.: RWI\_TP\_EPI0011 Revision 2 Reference: RWI\_WI\_EPI0005

ARMGO Pharma, Inc. RYR1-RM Study Version 4.0 dated 10-SEP -2024 Protocol/Study No.: CL-EPI-001

Page 20 of 64

## 3. OBJECTIVES AND ENDPOINTS

## Table 1. Study objectives and endpoints

Objectives	Endpoints
Primary	
To determine the extent to which muscle strength is affected in participants with RYR1-RM with autosomal dominant mutations and describe measurements over time.	
 
Weight-scaled muscle strength as measured by QMA (measuring participant's shoulder abduction, elbow flexion and extension, and knee flexion and extension), MMT (measuring participant's neck flexion), and HHD (measuring participant's neck flexion)
 
Muscle strength will also be measured by additional tests:10-MWT, 1-Minute-Sit-to-Stand Test, and Stair Climb Test.
 

Secondary	
To determine the extent to which fatigue and physical function is affected in participants with RYR1-RM with autosomal dominant mutations.	PROMIS Fatigue, PROMIS-PF and, IPAQ questionnaire outputs.
To describe the demographic and clinical characteristics of participants with RYR1 -RM with autosomal dominant mutations in the real-world setting.	
 
Demographics and clinical characteristics (medication use including current and prior medications, medical history, full physical, neurological, and functional examination, height, weight, BMI, and vital signs).
 
Symptom diary.
 

Exploratory	
• To evaluate the Syde® device for use in participants with RYR1 -RM with autosomal dominant mutations.	Syde® device use in participants with RYR1- RM through objective assessment of activity (e.g., stride velocity when walking and climbing stairs).

10-MWT, 10- Meter Walk Test; BMI, Body mass index; IPAQ, International Physical Activity questionnaire; PROs, patient-reported outcomes; PROMIS, Patient-Reported Outcomes Measurement Information System; PROMIS-PF, Patient-Reported Outcomes Measurement Information System-Physical Function; *RYR1*-RM, Ryanodine receptor isoform 1-related congenital myopathies; QMA, Quantitative Muscle Assessment.

## 4. STUDY DESIGN

## 4.1 Study Description

This is an observational, prospective, multi-centre study to assess muscle strength in participants with *RYR1*-RM with autosomal dominant mutations to determine the optimal muscle strength measurement endpoints. The study will be conducted at participating sites in Europe and the United Kingdom.

Template No.: RWI\_TP\_EPI0011 Revision 2 Reference: RWI\_WI\_EPI0005

[figure not shown]

ARMGO Pharma, Inc. RYR1-RM Study Version 4.0 dated 10-SEP -2024 Protocol/Study No.: CL-EPI-001

Page 21 of 64

The study will consist of up to four visits: each taking place 30 days apart with the following windows of deviation to allow for flexibility in participant scheduling defined as follows: Screening Visit (0 days), Visit 1 (±3 days), Visit 2 (-14/ +3 days) and End of Study Visit (-14/ +3 days). The length of time for a patient to complete all four visits would range from a minimum of 59 days to a maximum of 99 days. Index date is defined as the date of the participant's Screening Visit. Six muscle movements dependent primarily on the proximal muscles will be tested to inform optimal endpoints for further studies. At each study visit including Screening, participants' shoulder abduction, elbow flexion and extension, and knee extension and flexion will be measured using QMA testing. Neck flexion will be measured using HHD and MMT. The study's overall duration will be about 9 months, from data collection to analysis and reporting of results. A schematic of the study design is presented in Figure 1.

Figure 1 Study Design

10-MWT, 10-Meter Walk Test, AE, adverse event; HHD, Hand-held dynamometry; IPAQ, International Physical Activity questionnaire; MMT, Manual Muscle Test; PROMIS, Patient-Reported Outcomes Measurement Information; RYR1 RM, Ryanodine receptor isoform 1-related congenital myopathies, SAE, serious adverse event; QMA, Quantitative Muscle Assessment.

Template No.: RWI\_TP\_EPI0011 Revision 2 Reference: RWI\_WI\_EPI0005

ARMGO Pharma, Inc. RYR1-RM Study Version 4.0 dated 10-SEP -2024 Protocol/Study No.: CL-EPI-001 Page 22 of 64

Data will be extracted from the participants' medical records (both paper and/or electronic) at the Screening Visit (at site) and entered in an electronic case report form (eCRF). This data will be used to capture the participant's full medical history (starting from the earliest record available), including the date of *RYR1*-RM diagnosis, comorbidities, and medication use. Medical records may also be used to assess other clinical characteristics, including vital signs, forced vital capacity (FVC) and electrocardiogram (ECG) (if available in the participants' medical records within 12 months prior to the Screening Visit).

Data collected at study visits will be manually entered into the eCRF. The following data will be collected from participants at relevant time points for study assessments and procedures:

- Medical history (including biopsy details, if performed);
- Medication use (including all current and prior medications to treat symptoms of *RYR1*-RM);
- Full physical, neurological, and functional examination;
- Vital signs (heart rate, blood pressure, respiratory rate, temperature), FVC sitting and supine, and ECG;
- Strength measurements by QMA (shoulder abduction, elbow flexion and extension, knee flexion and extension), MMT (neck flexion), and HHD (neck flexion);
- 10 Meter Walk Test;
- 1-Minute Sit-to-Stand:
- Stair Climb Test; and
- PROMIS Fatigue, PROMIS-PF, IPAQ, and symptom diary.

Participants will be given periods of rest in between tests to reduce their burden. Ideally, all visits should be conducted in the morning to minimise the impact of the participant's daily activities on their energy levels, cognitive function, and mood. However, the actual timing of the visits may vary according to the capacity of the sites.

For details on data collected at each visit refer to the data collection schedule table in Section 4.5.

## 4.2 Study Population

The study will aim to enrol up to 20 participants from neurology clinics at study centres in Europe and the United Kingdom over a 2.5-month enrolment period.

#### 4.2.1 Inclusion Criteria

The following criteria must be met to be enrolled in the study:

Template No.: RWI\_TP\_EPI0011 Revision 2 Reference: RWI\_WI\_EPI0005

ARMGO Pharma, Inc. RYR1-RM Study Version 4.0 dated 10-SEP -2024 Protocol/Study No.: CL-EPI-001 Page 23 of 64

- Male and female patients (biological sex\*) aged 18 years or older at Screening;
- Confirmed genetic diagnosis of *RYR1*-RM with autosomal dominant mutation and supporting clinical phenotype with demonstrable proximal weakness on at least one of the baseline study assessments;
- Evidence of at least one demonstratable muscle/motor function deficit assessed through Manual Muscle Testing (MMT) and scored using the Medical Research Council (MRC) Scale for muscle strength (17) on physical examination (see MRC scale described in Table 5);
- Able to walk 10 meters, with or without assistance e.g., with a cane (assessed using the 10 Meter Walk Test);
- Willingness and ability to comply with scheduled visits and study procedures;
- Willingness to be fitted with the Syde® device at Screening Visit (for inclusion in the exploratory objective analysis only); and
- Able to provide written informed consent and understand the study procedures in the informed consent form (ICF).

\*Biological sex of male or female is required for study inclusion based on the available normative values for the tests conducted, but all gender identities are eligible for inclusion in the study.

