#### 4.4 Outcome Definition and Measures

#### 4.4.1 Endpoint Measures

#### 4.4.1.1 Primary Endpoint Measures

Absolute measurements at each study visit and changes in muscle strength measured by QMA, HHD, and MMT will be assessed between Screening, each visit as well as between consecutive visits. QMA will be used to assess knee flexion and extension, elbow flexion and extension, and shoulder abduction. Neck flexion will be measured using HHD and MMT (Error! Reference source not found.). Additional tests that will be performed to measure muscle strength include the 10-MWT, 1-Minute-Sit-to-Stand Test, and Stair Climb Test. The Screening measurement will be the baseline for the study. All tests should be conducted at the same time of day and in a standardized order for all participants across the study sites as follows:

- a) QMA;
- b) HHD;
- c) MMT;
- d) 10-MWT;
- e) 1-Minute-Sit-to-Stand Test; and lastly
- f) Stair Climb Test.

Table 2. Method of assessment for muscle strength measurements

Method of assessment	Muscle movement
	Knee Extension
	Knee Flexion
QMA a	Elbow Extension
	Elbow Flexion
	Shoulder Abduction
HHD	Neck Flexion
MMT	Neck Flexion

HHD, Hand-Held Dynamometry; MMT, Manual Muscle Testing; QMA, Quantitative Muscle Assessment.

Template No.: RWI\_TP\_EPI0011 Revision 2 Reference: RWI\_WI\_EPI0005

<sup>a For QMA, each muscle movement will be tested on both limbs (noting which is the dominant limb and starting with the dominant limb).

ARMGO Pharma, Inc. RYR1-RM Study Version 4.0 dated 10-SEP -2024 Protocol/Study No.: CL-EPI-001 Page 26 of 64

a) Quantitative Muscle Assessment (QMA)

QMA is a quantitative muscle testing (QMT) method that will be used to assess knee flexion and extension, elbow flexion and extension, and shoulder abduction. QMA is designed to measure Maximum Voluntary Isometric Contraction (MVIC), an objective and validated measure of muscle strength. MVIC has been adopted for the measurement of muscle strength in participants with neuromuscular disorders across several studies (18), and it has been shown to be a more reliable assessment tool than MMT methods. (19) MVIC can be measured using a strain gauge (which is attached to the participant on a standard plinth at one end and to orthopaedic bars at the other) or an HHD.

The QMA system consists of the following items (18, 20):

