Anti-gravity	Supine, with arms by the side and head supported on a table	Standing next to the participant's head, with the testing hand placed on the participant's forehead	The participant lifts their head off the table by flexing the neck and tucking the chin. The tester applies resistance at the forehead in the direction of capital and cervical extension and may position a hand underneath the subject's head for protection or offer additional stabilization across the abdomen (if needed)
Gravity-eliminated (for weaker participants only)	Side lying, with head supported on the table and arms by the side	Supporting the participant's head to prevent cervical side bending, and providing stabilization at the anterior shoulder as needed	Participant is instructed to flex their head and neck towards their chest

MMT, Manual Muscle Testing. Source: MMT manual (32).

The MMT assessment of neck flexion will be conducted at Screening, Visit 1, Visit 2, and End of Study Visit. Three measurements of neck flexion will be performed at each visit, and both the individual and average scores of the three measurements will be described.

Although both MMT and HHD are designed to measure the same underlying concept, the literature only suggests moderate correlations between their measurements of neck flexion. (10) Such discrepancy may be explained by the fact that MMT has decreased sensitivity and specificity in detecting mild weakness compared to HHD. Furthermore, the grading system of MMT is subjective and may vary according to the strength of the examiner. (33, 34)

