# 4.5.1 Screening Visit

The following data will be collected at the Screening Visit for all enrolled participants (listed in the order in which they will be collected during the visit):

- Informed consent;
- Inclusion/Exclusion (including MMT to assess muscle/motor function deficit, 10-MWT to assess ability to walk, and FVC to assess pulmonary dysfunction);
- Demographics (medical records);
- Medical history (medical records);
- Medication use (medical records);
- Vital signs and ECG (medical records or primary data collection; note that FVC will be evaluated as part of the assessment of the exclusion criteria);
- Strength measurements using QMA and HHD (note that MMT will be conducted at the start of the Screening Visit as part of the assessment of the inclusion criteria);
- 1-Minute Sit-to-Stand Test;
- 4SCT:
- Full physical, neurological, and functional examination;
- PROMIS Questionnaires;
- IPAO:
- Syde® device fitting;
- Symptom diary (initiation); and
- AE/SAE.

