# 6.2 Data Analyses

#### **6.2.1** General Considerations

All computations and generation of tables, listings, and data for figures will be performed using SAS® version 9.2 or higher (SAS Institute, Cary, NC, USA).

Prior to database lock, a detailed, finalized SAP will be completed and approved. The SAP will contain a more comprehensive description of the methodology for the statistical analyses than outlined in this protocol. The SAP will provide full details of the analyses, the data displays, and the algorithms to be used for data derivations.

Continuous variables will be described using descriptive statistics of central tendency (median and mean) and dispersion (standard deviation, interquartile range, maximum and minimum values). Categorical variables will be summarized as counts and proportions of the total study population. The 95% confidence interval will be presented for estimates of means and proportions. Descriptive statistics for both continuous and categorical variables will be based on participants with non-missing responses to the variable. Frequencies and percentages of missing values in each variable will be reported.

Whenever applicable, the endpoints will be summarized by each visit and across the overall study period (e.g., average endpoint across study visits). Furthermore, the absolute change in the endpoints between (i) Screening and each follow-up visit, and (ii) between each consecutive follow-up visit will be calculated and summarized with descriptive statistics.

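### The eligibility MMT at Screening also serves as the baseline for the neck-flexion MMT endpoint, and it is taken outside the fixed test order

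*Protocol*

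**What the plan says.** **Entry.** Section 4.2.1 of the Protocol asks for a confirmed genetic diagnosis with a "supporting clinical phenotype with demonstrable proximal weakness on at least one of the baseline study assessments". A further criterion asks for at least one deficit on MMT, graded on the MRC scale on physical examination, with a pointer to Table 5.

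**Outcome.** Table 1 gives the primary objective as "To determine the extent to which muscle strength is affected in participants with RYR1-RM with autosomal dominant mutations and describe measurements over time" and lists neck-flexion MMT among the primary endpoints. The MMT part of Section 4.4.1.1 adds: "Three measurements of neck flexion will be performed at each visit".

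**Timing at Screening.** Section 4.5.1 states that its list follows the order of collection. MMT, the 10-MWT and FVC sit in the inclusion/exclusion step, directly after consent. The later strength entry names only QMA and HHD, with the remark "note that MMT will be conducted at the start of the Screening Visit as part of the assessment of the inclusion criteria". The 10-MWT does not reappear either. The Screening list in the synopsis is the same.

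**Baseline and change.** Section 4.4.1.1: "The Screening measurement will be the baseline for the study". Section 6.2.1 plans "the absolute change in the endpoints between (i) Screening and each follow-up visit", and also change between consecutive follow-up visits.

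**Order.** Section 4.4.1.1 sets one order for everyone at all sites: QMA, HHD, MMT, 10-MWT, sit-to-stand, stair climb.

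**Limitations.** Section 6.2.4.1 puts doubts about representativeness down to the small sample and non-random sampling. It does not mention entry on weakness in the study's own tests.

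**The concern.** A reading used to admit someone is not a neutral baseline for that person. Patients graded too low on the day get in, and patients graded too high may not. At the next visit the error is drawn afresh, so the mean of the admitted group rises although nobody has become stronger. On a scale with a ceiling at grade 5, this appears as participants moving from 4 to 5. Some misgrading is to be expected, since the protocol itself says that MMT grading depends on the examiner's judgement and strength.

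The order of tests is a second problem for the same comparison. A baseline taken before the other strength tests is compared with follow-up readings taken after them.

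What is at stake is the time course of one primary endpoint in a study whose results are meant to tell a Phase II trial what baseline and variability to expect.

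**Working it through.** **1. Is it the same reading?** Section 4.5.1 gives one MMT session for neck flexion at Screening, in the eligibility step. Section 4.4.1.1 makes Screening the baseline, and Section 6.2.1 measures change from it. So the session that decides entry also supplies the baseline.

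**2. Which movement qualifies?** For neck flexion:
- The remark in Section 4.5.1 explains why MMT is absent from the strength entry, so the session moved forward is the endpoint MMT, which Table 2 limits to neck flexion.
- Table 5, to which the criterion points, is titled for neck flexion.
- The examination of other muscles (Appendix 11.1) comes after the stair climb.

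Against: the criterion names no muscle and refers to physical examination, and Appendix 11.1 lists many other muscles. The text leans towards neck flexion but does not settle it.

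**3. Size of the drift.** The protocol gives no figure to reproduce: no SD, no reliability, no share at grade 5. The following inputs are therefore assumptions.
- Latent strength at visit v: X_v = T + E_v, with Var(T) = r and Var(E_v) = 1 − r. Reliability r is 0.6 to 0.9.
- Grade 5 if X_v > c, where P(X_v > c) = p. The share p at grade 5 among unselected patients is 0.1 to 0.5.
- Grade 4 reaches 1.5 below c, grade 3 a further 1.0, and grade 2 lies below that.
- True scores of different muscles correlate 0.5. There is no true change. Each run has 400,000 simulated patients, with one visit-level grade per visit.

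Drift = mean(follow-up grade − Screening grade) among those selected. Its size relative to the standard error at n = 20 is drift / (SD of change / √20).

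Neck flexion below grade 5 required for entry:

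| p | r | Mean Screening grade | Drift | SD of change | Drift / SE | At grade 5 at follow-up |
|---|---|---|---|---|---|---|
| 0.1 | 0.9 | 3.42 | +0.033 | 0.52 | 0.29 | 3% |
| 0.1 | 0.6 | 3.42 | +0.075 | 0.79 | 0.43 | 7% |
| 0.3 | 0.9 | 3.73 | +0.089 | 0.49 | 0.82 | 9% |
| 0.3 | 0.6 | 3.73 | +0.193 | 0.71 | 1.22 | 18% |
| 0.5 | 0.9 | 3.85 | +0.144 | 0.48 | 1.35 | 14% |
| 0.5 | 0.6 | 3.85 | +0.309 | 0.66 | 2.11 | 30% |

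Last row: 0.309 / (0.66 / √20) = 0.309 / 0.148 ≈ 2.1. At Screening nobody in this group is at grade 5, by selection.

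A deficit in any one of 14 muscles suffices: drift −0.001 to +0.003. No selection: within ±0.001.

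**Check by hand.** Take only grades 4 and 5, with half the patients truly at 5 and a 10% chance of misgrading by one. Share admitted: 0.5 × 0.1 + 0.5 × 0.9 = 0.50. Of these, 0.05 / 0.50 = 0.10 are truly grade 5. Graded 4 again next time: 0.10 × 0.1 + 0.90 × 0.9 = 0.82. So 18% move to grade 5 and the mean rises by 0.18. This cruder model gives the same direction and order of size.

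**4. Test order.** At follow-up, in the order of Section 4.4.1.1, MMT comes after QMA and HHD. If the three QMA trials are per limb, that is 5 movements × 2 limbs × 3 = 30 maximal contractions, plus 3 HHD neck flexions: 33 efforts. In the Screening order of Section 4.5.1 none of these comes first. The 10-MWT is displaced in the same way. Fatigue would be expected to lower follow-up readings relative to Screening, against the selection drift, so the two could partly cancel. The protocol gives nothing from which to size the fatigue effect.

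**The case against.** The strongest reply is that the drift is conditional. If a deficit in any of many muscles can admit a patient, it vanishes. That stands, and the range must be read with zero as its lower end. But the uncertainty comes from the protocol's own text, and the order conflict exists under either reading.

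The three MMT readings per visit reduce trial-to-trial error. They do not remove error shared within a visit or due to the examiner. The rest periods planned in Section 4.1 lessen the fatigue difference but do not make the positions equal. Changes between follow-up visits are already planned, which keeps the analysis cost low, but they do not repair the Screening baseline. That the study is descriptive, with up to 20 participants and no hypothesis tests, limits the harm.

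Stronger readings are tempting, and the documents do not support them:
- *A reader might infer that the finding of weakness is true by construction.* Table 1 asks for the extent of weakness. The entry rule guarantees only that some deficit exists. It does not set the deficit in any given QMA, HHD or functional measure. Summaries of enrolled participants are not biased for those participants, and Section 6.2.4.1 already concedes limited generalisability.
- *A reader might infer that the drift would pass for the learning effect.* Section 2 ties that effect to repeated QMA measurements, not to MMT.
- *A reader might want other qualifying muscles.* Selecting on shoulder or thigh muscles would select on movements that QMA measures, so selection on the outcome would move rather than end.

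**Conclusion.** The point holds in a limited form. One MMT session at Screening serves as entry test and as baseline for a primary endpoint, and its place contradicts the fixed order.

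If neck flexion qualifies, the upward drift is roughly +0.03 to +0.31 MRC grade, or 0.3 to 2.1 standard errors at n = 20, with 3% to 30% of participants reaching grade 5 without real change. If any of many muscles can qualify, it is about zero. These figures rest on the assumed reliability, share at grade 5, grade spacing and between-muscle correlation. The order conflict rests on the text alone; its effect cannot be sized. This is a cheap improvement to one endpoint's baseline and to the order of two tests, not a flaw in the study as a whole.

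**What to change.** 1. In Section 4.5.1 and the matching synopsis list, give the three endpoint neck-flexion MMT measurements their own slot after HHD, separate from the MMT that decides entry. The entry criterion need not change.
2. Reconcile Sections 4.4.1.1 and 4.5.1 on the order of tests at Screening, including where the endpoint 10-MWT is done.
3. For neck-flexion MMT, judge stability from the changes between follow-up visits already planned in Section 6.2.1, shown beside change from Screening. This also covers what item 1 cannot: a repeat on the same day, perhaps by the same examiner, may share some error with the qualifying reading. The drift is about zero only if the two errors are independent.
4. Add to Section 6.2.4.1 that entry selects on weakness in the study's own assessments, so the results describe patients with demonstrable weakness.

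The cost is a few minutes of repeat MMT at Screening and some protocol wording. No new type of test or analysis is needed.
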